7.2.1.3 Biomarkers

Biomarker data and parameters of a subject will be included in the statistical biomarker analyses if they are not flagged for exclusion due to a protocol deviation relevant to the evaluation of biomarkers (to be decided no later than in the Report Planning Meeting) or due to non-evaluability (as revealed during data analysis, based on the criteria specified below).

Relevant protocol deviations may be as listed for pharmacokinetics in Section [7.2.1.2](#). Biomarker data and/or parameters of a subject may for example be considered as non-evaluable, if the time-matched blood PK sample is considered as non-evaluable.

Exclusion of a subject's data will be documented in the CTR. Biomarker data and parameters of a subject which is flagged for exclusion will be reported with its individual values but will not be included in the statistical analyses.

7.2.2 Primary endpoint analyses

SRD part

The primary endpoint as specified in Section [2.1.2](#) will be derived according to BI standards. The analysis will be based on the treated set (TS) and will be descriptive in nature.

FE part

Primary analyses:

The statistical model used for the analysis of the primary endpoints as specified in Section 2.1.2 will be an analysis of variance (ANOVA) model on the logarithmic scale. That is, the PK endpoints will be log-transformed (natural logarithm) prior to fitting the ANOVA model. This model will include effects accounting for the following sources of variation: sequence, subjects within sequences, period and treatment. The effect 'subjects within sequences' will be considered as random, whereas the other effects will be considered as fixed. The model is described by the following equation:

$$y_{ijkm} = \mu + \zeta_i + s_{im} + \pi_j + \tau_k + e_{ijkm}, \text{ where}$$

y_{ijkm} = logarithm of response measured on subject m in sequence i receiving treatment k in period j ,

μ = the overall mean,

ζ_i = the i^{th} sequence effect, $i = 1, 2$,

s_{im} = the effect associated with the m^{th} subject in the i^{th} sequence,
 $m = 1, 2, \dots, n_i$

π_j = the j^{th} period effect, $j = 1, 2$,

τ_k = the k^{th} treatment effect, $k = 1, 2$ (i.e. R, T)

e_{ijkm} = the random error associated with the m^{th} subject in sequence i who received treatment k in period j .

where $s_{im} \sim N(0, \sigma_B^2)$ i.i.d., $e_{ijkm} \sim N(0, \sigma_W^2)$ i.i.d. and s_{im} , e_{ijkm} are independent random variables.

Point estimates for the ratios of the geometric means (T/R) for the primary endpoints and their two-sided 90% confidence intervals (CIs) will be provided.

For each endpoint, the difference between the expected means for $\log(T)$ - $\log(R)$ will be estimated by the difference in the corresponding adjusted means (Least Squares Means).

Additionally their two-sided 90% confidence intervals will be calculated based on the residual error from the ANOVA and quantiles from the t-distribution. These quantities will then be back-transformed to the original scale to provide the point estimate and 90% CIs for each endpoint.

Further exploratory analyses:

The same statistical model as stated above will be repeated for the primary endpoints but with all sources of variation ('sequence', 'subjects within sequences', 'period', 'treatment') considered as fixed effects.

In addition to the model-based approach all parameters will be calculated and analysed descriptively.

7.2.3 Secondary endpoint analyses

SRD part

Primary analyses:

The secondary endpoints (refer to Section [2.1.3](#)) will be analysed descriptively. Analyses will be performed for the parent drug.

Further exploratory analyses

Dose proportionality will be explored via graphical checks and if applicable via the power model stated below. The analysis will be performed for the pharmacokinetic endpoints specified in Section 2.1.3.

The power model describes the functional relationship between the dose level and PK endpoint on the log scale via

$$y_{km} = \log(x_{km}) = \mu + \beta \cdot \log(D_k) + e_{km},$$

where

- y_{km} logarithm of response (PK parameter) measured on subject m receiving dose k,
- μ the overall mean,
- β slope parameter of linear regression line,
- D_k level of dose k, $k=1, \dots, 7$,
- e_{km} the random error associated with the m^{th} subject who was administered dose k ($e_{km} \sim N(0, \sigma^2)$ iid).

The slope parameter β together with its two-sided 90% confidence interval will be estimated. Additionally, the r-fold change $r^{\beta-1}$ together with its 90% CI will be derived.

As some small doses at the beginning and/or some doses at the upper end might not contribute to the linear relationship between dose and PK, dose proportionality over the entire dose range investigated might not be shown. In that case an attempt will be made to identify a subrange of at least 3 consecutive doses where dose proportionality can be concluded.

FE part

The secondary endpoint (refer to Section [2.1.3](#)) will be calculated according to the relevant SOP of the Sponsor and will be assessed statistically using the same methods as described for the primary endpoints.

7.2.4 Further endpoint analyses

7.2.4.1 Pharmacokinetic analyses

Further PK endpoints will be analysed descriptively for both parts separately.

7.2.4.2 Biomarker analyses

Analysis of pharmacodynamics parameters is only applicable for the SRD part.

The PD endpoint listed in Section [2.2.2](#) as well as possible further PD endpoints specified in the TSAP will be analysed descriptively by dose group over time. The placebo group will consist of all subjects treated with placebo in the SRD part.

7.2.5 Safety analyses

Safety will be assessed as defined by the endpoints listed in Section [2.1.2](#) and [2.2.2](#) based on the treated set (TS). Safety analyses will be descriptive in nature and will be based on BI standards.

For all analyses the treatment actually administered (= treatment at onset) to the subject will be used (any deviations from the randomised treatment will be discussed in the minutes of the Report Planning Meeting).

Treatments will be compared in a descriptive way. The placebo group in the safety evaluation will consist of all subjects treated with placebo, regardless of the dose group in which they were treated. The test treatment groups will be compared to the placebo group in a descriptive way. Tabulations of frequencies/proportions will be used for the evaluation of categorical (qualitative) data, and tabulations of descriptive statistics will be used to analyse continuous (quantitative) data.

Measurements (such as ECGs, vital signs, or laboratory parameters) or AEs will be assigned to treatments (see Section [4.1](#)) based on the actual treatment at the time of the measurement or on the recorded time of AE onset (concept of treatment-emergent AEs). Therefore, measurements performed or AEs recorded prior to intake of trial medication will be assigned to the screening period, those between the trial medication intake and end of REP (see Section [1.2.2](#)) will be assigned to the treatment period. Events occurring after the REP but prior to trial termination date will be assigned to 'follow-up'. These assignments including the corresponding time intervals will be defined in detail in the TSAP. Note that AEs occurring after the last per protocol contact but entered before unblinding the trial will be reported to Pharmacovigilance only and will not be captured in the trial database.

Additionally, further treatment intervals (called analysing treatments) may be defined in the TSAP in order to provide summary statistics for other than above periods, such as combined

treatments, on-treatment totals, or periods without treatment effects (such as screening and post-study intervals).

Adverse events will be coded using the Medical Dictionary for Regulatory Activities (MedDRA). Frequency, severity, and causal relationship of AEs will be tabulated by treatment, system organ class and preferred term. SAEs, AESIs (see Section 5.2.6.1) and other significant AEs (according to ICH E3) will be listed separately.

Previous and concomitant therapies will be presented per treatment group without consideration of time intervals and treatment periods.

Laboratory data will be compared to their reference ranges. Values outside the reference range will be highlighted in the listings. Additionally, differences from baseline will be evaluated.

Vital signs or other safety-relevant data will be assessed with regard to possible on-treatment changes from baseline.

The ECG variables QT, PR, QRS, and RR obtained from the centralised evaluation of 12-lead ECG recordings will be the basis for the derivation of quantitative and categorical ECG endpoints with regard to QT/QTc interval, HR, PR interval and QRS duration. These endpoints and their analyses will be described in the TSAP.

7.2.6 Other analysis

SRD part

An exploratory analysis of the relationship between pharmacokinetic and pharmacodynamic parameters is planned.

A population PK and/or PK/PD analysis may be performed at the project level using a nonlinear mixed effects modelling approach. Further details will be specified in an appropriate pharmacometric analysis plan; this analysis will not be part of the CTR.

The relationship between plasma concentrations and ECG endpoints will be investigated in an exploratory manner. Further details will be specified in the TSAP.

7.2.7 Interim analyses

No formal interim analysis is planned.

Prior to each dose escalation a documented safety review will be performed as described in Section 3.1. To support dose escalations a preliminary analysis of PK parameters (at least AUC₀₋₂₄ and C_{max} of BI 3000202), provided as individual values and geometric means, will be performed for

- Dose levels 1, 2 and 3 (n) before proceeding to dose level 3, 4 and 5 (n+2)
- Dose levels 5 and 6 (n) before proceeding to the next dose level 6 and 7 (n+1)

(Note: Data from the first cohorts of the above-mentioned dose levels will be sufficient as long as the data from at least 3 subjects on active treatment were available.)

The pharmacokinetic parameters C_{\max} and AUC_{0-24} for BI 3000202 will be calculated according to the relevant BI internal procedure. In contrast to the final PK calculations, the preliminary, exploratory analysis will be based on planned sampling times rather than on actual times, regardless of whether actual times were within the time windows or not. Therefore, minor deviations may occur between preliminary and final results.

The preliminary analysis will provide individual and mean concentration/effect-time profiles and summary statistics of individual values without subject identification information.

Available information on dose linearity from preceding dose groups will be considered when estimating C_{\max} and AUC_{0-24} values to be expected for the next higher dose to be administered.

Additional PK preliminary analysis may be performed if requested by the Clinical Trial Leader, the investigator, or Trial Clinical Pharmacologist.

No inferential statistical interim analysis is planned. However, after completion of each dose group the investigator (or his or her deputy) is allowed to postpone further dose progression until a preliminary analysis of the data has been performed.

A preliminary, exploratory analysis of the PD parameters may be performed based on evaluable data prior to database lock to inform other activities during the development of substance.

A preliminary, exploratory analysis of the PK parameters (AUC_{0-tz} , $AUC_{0-\infty}$ and C_{\max} of substance) may be performed based on all evaluable data after last subject out and prior to data base lock. This may be necessary, e.g., in case the information is needed to inform other activities during the development of substance such as concomitant treatment restrictions in other studies. In contrast to the final PK calculations, the preliminary, exploratory analysis will be based on planned sampling times rather than on actual times, regardless of whether actual times were within the time windows or not. Therefore, minor deviations of preliminary and final results may occur. Results will be provided as individual values and geometric means as well as the adjusted gMean ratios determined according to the planned primary analysis. The preliminary, exploratory results will be distributed to the trial team. No formal preliminary PK report will be written.

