This exposure cap is defined for the expected (predicted) gMean values of a dose level as estimated based on preliminary PK data of preceding dose group(s). That means, a dose level will only be administered if expected gMean values for C_{\max} and AUC_{0-24} do not exceed these exposure values (see dose escalation stopping criteria in Section [3.3.4.3](#)).

In addition, due to inter-individual variability, actual systemic exposure in individual subjects may exceed these values. However, as soon as the actual observed exposure in one subject exceeds the maximum acceptable exposure, dose escalation will be stopped (see Section [3.3.4.3](#)).

[REDACTED]

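### Level 4 is the only planned dose level below the top one with no mandatory preliminary PK read, so the one-subject exposure stop has no required data there

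*Protocol*

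**What the plan says.** Protocol Section 7.2.7 requires a preliminary analysis of AUC0-24 and Cmax, as individual values and geometric means, on this schedule: "Dose levels 1, 2 and 3 (n) before proceeding to dose level 3, 4 and 5 (n+2" and "Dose levels 5 and 6 (n) before proceeding to the next dose level 6 and 7 (n+1". Data from the first cohorts of a listed level are "sufficient as long as the data from at least 3 subjects on active treatment were available".

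Two further provisions in the same section are permissive. "Additional PK preliminary analysis may be performed if requested by the Clinical Trial Leader, the investigator, or Trial Clinical Pharmacologist", and after each dose group the investigator "is allowed to postpone further dose progression until a preliminary analysis of the data has been performed".

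The exposure rules are in Section 1.3.3 and are repeated in Sections 1.4.2 and 3.3.4.3. One concerns the group: "a dose level will only be administered if expected gMean values for" Cmax and AUC0-24 stay within the cap. The other concerns the individual: "as soon as the actual observed exposure in one subject exceeds the maximum acceptable exposure, dose escalation will be stopped". Neither has an exception for any dose level.

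Section 3.1 lets the next group start only if no stopping criterion has been met. For the PK part of the safety review it refers to Section 7.2.7 and adds no level of its own.

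**The concern.** The individual exposure stop can act only on exposures that someone has looked at. If the plan never requires level 4 PK to be read, the trial can follow the protocol to the letter and still dose levels 5, 6 and 7 while a level 4 value above the cap sits unanalysed.

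This is a first-in-human trial. Section 1.4.2 says the cap was set from toxicity findings and names QT prolongation as a risk indicated by nonclinical data. The group-level check does not stand in for the individual stop, because Section 1.3.3 itself says that "due to inter-individual variability, actual systemic exposure in individual subjects may exceed these values". Section 7.2.7 gives no reason for leaving level 4 out. Parts of the dose-escalation rationale are redacted, so a reason may exist that the public text does not show.

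**Working it through.** **Inputs.** Seven planned levels, each with 6 active subjects (Section 3.1). Mandatory reads: n+2 for levels 1, 2 and 3, and n+1 for levels 5 and 6, with at least 3 active subjects per read (Section 7.2.7).

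**Step 1: reproduce the schedule.** The n+2 rule gives 1→3, 2→4, 3→5. The n+1 rule gives 5→6, 6→7. Both agree with the target levels printed in Section 7.2.7.

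**Step 2: mandatory reads in hand before each step.**

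| Before dosing level | Mandatory reads in hand | Lower levels not read |
|---|---|---|
| 2 | none | 1 |
| 3 | 1 | 2 |
| 4 | 1, 2 | 3 |
| 5 | 1, 2, 3 | 4 |
| 6 | 1, 2, 3, 5 | 4 |
| 7 | 1, 2, 3, 5, 6 | 4 |

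The level just below is also unread before levels 2, 3 and 4, but levels 1 to 3 are picked up one step later. Level 4 never is. Every step from level 3 upward has one PK gate.

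**Step 3: chance that the stop misses an exceeding subject.** Suppose k of the 6 active subjects exceed the cap, m of the 6 are read, and the exceeding subjects are equally likely to be any of the six. Then P(all missed) = C(6−m, k) / C(6, k). For k = 1:

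- level 4 as written, m = 0: 6/6 = 1.00
- any listed level at the minimum, m = 3: 3/6 = 0.50
- m = 4, the number of active subjects whose data Section 3.1 requires for escalation: 2/6 = 0.33
- m = 6: 0

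For m = 3 the probability is 3/15 = 0.20 if two subjects exceed and 1/20 = 0.05 if three do. These probabilities are conditional on an exceedance having occurred. They do not say how likely one is.

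**Step 4: effect of adding level 4.** Listing level 4 before level 5 (n+1) or before level 6 (n+2) leaves no level from 1 to 6 without a mandatory read. At the 3-subject minimum the miss probability at level 4 falls from 1.00 to 0.50.

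**Step 5: feasibility at the minimum intervals.** Section 3.1 gives 1 active subject in cohort 1 and 2 in cohort 2, so 1 + 2 = 3 active subjects are available before cohort 3. With cohort 1 at 0 h, the 22 h spacing puts cohort 2 at 22 h and cohort 3 at 44 h. Three days later, the first level 5 dose falls at 44 + 72 = 116 h. The 24 h sample of cohort 2 falls at 22 + 24 = 46 h, which leaves 116 − 46 = 70 h. The SRD flow chart has 15 plasma PK time points from predose to 24 h, so 15 × 3 = 45 samples would be assayed earlier.

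**The case against.** The strongest reply is that the omission follows from the design of the schedule. Each step from level 3 upward has one PK gate, and tightening the lag from n+2 to n+1 with one gate per step must skip one level. By the time a level 4 read would fall due under n+2, before level 6, a read of the higher level 5 is already mandatory. The stop is also written for observed exposure, so nothing in the text is contradicted. This stands as an explanation for forecasting group exposure. It does not serve the individual stop, because the level 5 read comes from other subjects and after level 5 has been dosed.

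A second reply is that other controls apply. Level 5 may be given only if its predicted gMean is within the cap. If exposure is roughly dose-proportional and the step from level 4 to level 5 is a factor f, the predicted level 4 gMean is then at most cap/f. A level 4 subject would have to exceed that prediction more than f-fold to breach the cap. A documented safety review is compulsory, cohorts are staggered, and Section 3.1 says preliminary PK is analysed regularly. These points stand and reduce the residual risk. None guarantees level 4 data: the remark on regular PK refers back to Section 7.2.7, and the mandatory PK behind the level 5 prediction stops at level 3.

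A reader might infer that the stop is secure at every level except 4. The documents do not support that. Three of six subjects suffice at each listed level, and levels 1 to 3 are also unread when the next dose is given. A reader might also infer that level 5 is reached with no PK gate at all. That is wrong too, because level 3 must be read first.

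**Conclusion.** The point holds for the seven planned levels in this limited form. Level 4 is the only level below the top one with no mandatory preliminary PK read: 0 of 6 active subjects, against at least 3 of 6 at levels 1, 2, 3, 5 and 6. The exposure stop therefore has no required level 4 data before levels 5, 6 or 7. Optional reads could supply them, so the right word is not required, rather than absent.

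The difference is one of degree. Given a single exceeding subject, the miss probability is 1.00 at level 4 and 0.50 at the other listed levels under a minimum read, assuming that subject is equally likely to be any of the six. How likely an exceedance is cannot be judged from the public documents, because doses, predicted exposures and caps are redacted. Level 4 may lie well below the cap. The importance is minor to moderate.

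**What to change.** In Section 7.2.7, extend the second bullet so that levels 4, 5 and 6 are read before levels 5, 6 and 7 respectively (n+1). Keep the minimum of 3 active subjects and the n+2 lag at levels 1 to 3. At the least, require the level 4 read before level 6 (n+2). If level 4 is left out on purpose, give the reason in that section. The n+1 version brings level 4 up to the standard of levels 5 and 6; it does not close the gap fully.

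No extra subjects or samples are needed. The costs are:

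- earlier assay of about 45 plasma samples
- a possible short delay before level 5. The 70 h window is the same length as that before levels 6 and 7 at the minimum intervals, but the protocol does not say that PK results are available within it
- a protocol amendment. The form in Section 11.1 gives changes in safety as an example of a substantial amendment, so approval before implementation may be required

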7.3 HANDLING OF MISSING DATA

7.3.1 Safety

It is not planned to impute missing values for safety parameters.

7.3.2 Pharmacokinetics

Handling of missing PK data will be performed according to the relevant BI internal procedure.

PK parameters that cannot be reasonably calculated based on the available drug concentration-time data will not be imputed.

7.3.3 Biomarkers

It is not planned to impute missing values for biomarker data, i.e. pharmacodynamic parameters.

7.4 RANDOMISATION

In the SRD part, subjects will be randomised within cohort 3 of each dose group in a 3:1 ratio (test treatment to placebo). Trial medication in cohorts 1 and 2 of each dose group will be administered in a fixed order (active - placebo - active - active; see Section [3.1](#)).

In the FE part, subjects will be randomised to one of the 2 treatment sequences in a 1:1 ratio. The block size will be documented in the CTR.

The sponsor will arrange for the randomisation as well as packaging and labelling of trial medication. The randomisation scheme will be generated using a validated system that uses a pseudo-random number generator and a supplied seed number so that the resulting allocation is both reproducible and non-predictable.

The randomisation scheme will contain additional blocks to allow for subject replacement (refer to Section [3.3.5](#)).

7.5 DETERMINATION OF SAMPLE SIZE

SRD part

It is planned to include a total of 56 subjects in this part of the trial. The planned sample size is not based on a power calculation. The size of 8 subjects per dose group (6 on active treatment, and 2 on placebo) is commonly used in single-rising dose studies of the present type and is in general considered as sufficient for the exploratory evaluation of single dose safety and pharmacokinetics.

Additional subjects may be entered to allow testing of additional doses on the basis of experience gained during the trial conduct (e.g. preliminary PK data), provided the planned and approved highest dose will not be exceeded and none of the stopping criteria apply. Thus, the actual number of subjects entered may exceed 56, but will not exceed 80 subjects entered.

The sample size of a specific dose group may increase by up to 2 subjects to enable dose escalation decision (see Section [3.3.5](#)).

FE part

It is planned to enter a total of 12 subjects in this part of the trial, because this sample size is considered sufficient for the exploratory investigation of relative bioavailability.

In total, $56 + 12 = 68$ subjects are planned to be included in this trial.

8. INFORMED CONSENT, TRIAL RECORDS, DATA PROTECTION, PUBLICATION POLICY, AND ADMINISTRATIVE STRUCTURE

The trial will be carried out in compliance with the protocol, the ethical principles laid down in the Declaration of Helsinki, in accordance with the ICH Harmonized Guideline for Good Clinical Practice (GCP), relevant BI Standard Operating Procedures (SOPs), the EU regulation 536/2014, and other relevant regulations. Investigators and site staff must adhere to these principles. Deviation from the protocol, the principles of ICH GCP or applicable regulations will be treated as 'protocol deviation'.

Standard medical care (prophylactic, diagnostic, and therapeutic procedures) remains the responsibility of the subject's treating physician.

The investigator will inform the sponsor immediately of any urgent safety measures taken to protect the trial subjects against any immediate hazard, as well as of any serious breaches of the protocol or of ICH GCP.

The Boehringer Ingelheim transparency and publication policy can be found on the following web page: trials.boehringer-ingelheim.com. As a rule, no trial results should be published prior to finalisation of the CTR.

The terms and conditions of the insurance coverage are made available to the investigator and the subjects and are stored in the ISF.

